16.3 Other Endpoint Analyses

16.3.1 Analysis of PK Endpoints

Predose samples that occur before the first drug administration will be assigned a time of 0 hours, as if the sample had been taken simultaneously with the study drug administration.

Pharmacokinetic concentrations which are erroneous due to a protocol deviation (as defined in the protocol), documented handling error or analytical error (as documented in the bioanalytical report) may be excluded from the PK analysis if agreed upon prior to performing a statistical analysis. In this case, the rationale for exclusion must be provided in the Clinical Trial Report (CTR). Any other PK concentrations that appear implausible to the Pharmacokineticist/PKPD Data Analyst must not be excluded from the analysis. Any implausible data will be documented in the CTR.

All statistical analyses and descriptive summaries of PK data will be performed on the PK Analysis Set. Pharmacokinetic concentrations will be listed for all subjects by treatment and fed/fasted group; concentrations excluded from the PK analysis will be flagged within the listing.

A listing of PK blood sample collection times by individual, as well as derived sampling time and time deviations, will be provided.

Plasma concentration data will be summarized descriptively for metformin as described in Section 11. Values below the LLOQ will be taken as zero for descriptive statistics of PK concentrations. Missing concentrations (e.g., no sample, insufficient sample volume for analysis, no result, or result not valid) will be reported and displayed generally as “N.R.”.

Samples that are collected outside the specified time windows will be included in the PK analysis but excluded from the concentration summary. The PK sampling collection schedule is presented in Table 6 below.

Table 6 Pharmacokinetic Sample Collection Schedule

| Trial Day | Period Day | Time of Blood Sample (hour) | Window Allowance (minute) |
|--|---|---|----------------------------------|
| 1 | 1 - Predose in Period 1 | Baseline blood draw (10 minutes prior to drug administration) | ±2 |
| 1 | 1 – Single dose administration and Washout begins | 0.5, 1, 1.5, 2, 2.5, 3, 3.5, 4, 5, 6, 8, 10, 14 | ±2 |
| 2 | 2 | 24, 36 | ±5 |
| 3 | 3 | 48 | ±5 |
| 4 – 7 | | | |
| 8 | 1-Predose in Period 2 | Baseline blood draw (10 minutes prior to drug administration) | ±2 |
| 8 | 1 – Single dose administration and Washout begins | 0.5, 1, 1.5, 2, 2.5, 3, 3.5, 4, 5, 6, 8, 10, 14 | ±2 |
| 9 | 2 | 24, 36 | ±5 |
| 10 | 3 | 48 | ±5 |
| 11-14 | | | |
| End of Trial (Day 15)/Premature Withdrawal | | 1-sample | ±30 |

Individual concentration-time profiles showing all subjects by treatment and fed/fasted group (i.e., individual subject overlay plots), and/or showing all treatment groups by subject (i.e., by-subject plots) will be created using the actual time points and the numeric concentration data. Arithmetic mean concentration-time profiles by treatment and fed/fasted group will be provided using scheduled (nominal) time points and the numeric concentration data. All concentration-time plots for PK data will be presented both on a linear and on a semi-logarithmic scale. Mean plots will include SD error bars when plotted on a linear scale.

16.3.2 Estimation of Individual Pharmacokinetic Parameters by Noncompartmental Analysis

For the PK analysis, predose sample concentrations that are below the LLOQ or that are missing will be assigned a numerical value of zero for the calculation of AUC. Any anomalous concentration values observed at predose will be identified in the CTR, and if the anomalous

predose concentration value is greater than 5.00% of the C_{max} in the profile, the profile will be included in the PK analysis, but the concentration data and the corresponding derived PK parameters will be excluded from summaries and inferential statistics as appropriate; handling of the data will be documented in the CTR.

Pharmacokinetic parameters will be calculated using standard noncompartmental methods. Pharmacokinetic parameters will be calculated and listed for all volunteers who provide sufficient concentration-time data. At least 3 valid, postdose concentration points will be required in the PK profile to obtain any PK parameter estimate.

Pharmacokinetic parameters will be calculated using the actual elapsed time since dosing, given with a precision of 14 significant digits. In cases where the actual sampling time is missing, calculations will be performed using the scheduled time. Otherwise, there will be no further imputation of missing data other than for a missing predose concentration as stated above.

For each subject in the PK Analysis Set the following PK parameters will be calculated for metformin, where appropriate:

| Symbol | Definition |
|------------------------------|---|
| $AUC_{0 \rightarrow t}$ | The AUC from time zero (= dosing time) to t_{last} at which the concentration is at or above the LLOQ. Calculated using the mixed log linear trapezoidal rule (linear up, log down). Units: ng*h/mL. |
| $AUC_{0 \rightarrow \infty}$ | The AUC from time zero (dosing time) extrapolated to infinity, based on the predicted value for the concentration at t_{last} , as estimated using the linear regression from λ_z determination. $AUC_{0 \rightarrow \infty} = AUC_{0 \rightarrow t} + C_{last \ pred} / \lambda_z$. Units: ng*h/mL. |
| $AUC_{extra\%}$ | The AUC from time t_{last} extrapolated to infinity given as percentage of $AUC_{0 \rightarrow \infty}$. $AUC_{extra\%} = (\text{extrapolated area} / AUC_{0 \rightarrow \infty}) * 100$. The predicted $AUC_{0 \rightarrow \infty}$ should be used. Units: %. |
| CL/f | The apparent total body clearance of drug following extravascular administration, taking into account the fraction of dose absorbed. $CL/f = \text{Dose}_{p.o.} / AUC_{0 \rightarrow \infty}$. The predicted $AUC_{0 \rightarrow \infty}$ should be used. The dose amount to be used for this calculation is 500 mg. Units: L/h. |
| C_{max} | Maximum observed concentration, taken directly from the observed concentration-time profile. Units: ng/mL. |
| t_{max} | The time to reach the maximum observed concentration (unless otherwise defined, take the first occurrence in case of multiple/identical C_{max} values). Units: h. |

| | |
|-------------|--|
| $t_{1/2}$ | Apparent terminal half-life. $t_{1/2} = \ln(2)/\lambda_z$. Units: h. |
| $V_{z/f}$ | The apparent volume of distribution during the terminal phase following extravascular administration, based on the fraction of dose absorbed. $V_{z/f} = \text{Dose}/(*AUC_{0 \rightarrow \infty} * \lambda_z)$ following single dose. Units: L. |
| λ_z | Terminal elimination rate constant. Determined from the terminal slope of the log-transformed concentration curve using linear regression on terminal data points of the curve. Units: h^{-1} . |

The following PK parameters will be calculated for diagnostic purposes and listed, but will not be summarized:

- The time interval (h) of the log-linear regression (λ_z lower, λ_z upper) to determine λ_z .
- Number of data points (N_λ) included in the log-linear regression analysis to determine λ_z .
- Goodness-of-fit statistic (Rsq) for calculation of λ_z .

The regression analysis should contain data from at least 3 different time points in the terminal phase consistent with the assessment of a straight line on the log-transformed scale. Phoenix WinNonlin best fit methodology will be used as standard. The last quantifiable concentration should always be included in the regression analysis, while the concentration at t_{max} and any concentrations <LLOQ which occur after the last quantifiable data point should not be used.

The Rsq should be ≥ 0.800 and the observation period over which the regression line is estimated should be at least two-fold the resulting $t_{1/2}$ itself. If these criteria are not met, then the rate constants and all derived parameters (e.g., $AUC_{0 \rightarrow \infty}$, $AUC_{extra\%}$, CL/f , $t_{1/2}$, and $V_{z/f}$) will be included in the parameter outputs and descriptive statistics but will be flagged and discussed appropriately. Any flags should be included in the study specific SDTM.

To ensure a reliable estimate of the extent of exposure in pivotal trials (e.g., BE), $AUC_{extra\%}$ should be less than or equal to 20.0%. If $AUC_{extra\%}$ is greater than 20.0%, all parameters derived using λ_z (i.e., λ_z , $t_{1/2}$, $AUC_{0 \rightarrow \infty}$, $AUC_{extra\%}$, $V_{z/f}$, and CL/f) will not be included in the calculation of descriptive statistics or statistical analyses.

The dose amount for IMP administered is that of the active, free drug substance only, and is synonymous with the measured analyte. No adjustment for the dose amount value of IMP will be applied when 'dose' is used in calculating PK parameters with formulas needing a dose value.

The Phoenix WinNonlin NCA Core Output will be provided in a separate listing.

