3.2 Glucophage Immediate Release

Glucophage® (Metformin hydrochloride: N,N-dimethylimidodicarbonimidic diamide hydrochloride; 1,1-dimethylbiguanide hydrochloride; N,N-dimethyldiguanide hydrochloride; N'-dimethylguanylguanidine hydrochloride) is an oral antihyperglycemic drug belonging to the class of biguanides and is not chemically or pharmacologically related to any other class of oral antihyperglycemic agents. The active ingredient, metformin, is the main representative of the biguanide class antihyperglycemic drugs.

Glucophage Immediate Release (GIR) tablet contains metformin hydrochloride, a white to off-white crystalline compound with a molecular formula of C₄H₁₁N₅ • HCl and a molecular weight of 165.62. Metformin hydrochloride is freely soluble in water and is practically insoluble in acetone, ether, and chloroform. It is an antihyperglycemic agent, which improves glycemic control in patients with T2DM. It does not stimulate insulin secretion and therefore does not produce clinically significant hypoglycemia. Metformin targets insulin resistance at the liver by decreasing hepatic glucose production and in muscle by enhancing peripheral glucose uptake and utilization, furthermore, it also delays intestinal glucose absorption. Metformin has been used for clinical management of diet-failed T2DM patients since 1959. Over this time, extensive experience has been gathered relating to the clinical use and safety of metformin. Currently, there are different approved pharmaceutical forms of Glucophage®, which have been developed to offer patients options that may fit their lifestyle and thereby improve compliance. Refer to the Investigator's Brochure (IB) [14] for further information about the nonclinical and clinical programs of GIR and Guidance for the Investigator.

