5.2 Discussion of Trial Design

This is a single-center, open-label, 2-way crossover design. This trial has been designed considering the latest regulatory guidelines on BE design issued by Chinese Food and Drug Administration in March 2016 [15]. In this new guideline, it is recommended to design a clinical BE study in accordance with the intended clinical practice and label of the test and reference product.

According to these guidelines, it is justified to conduct the trial in a crossover design, allowing for each subject to serve as his/her own control. The trial will be performed in an open-label manner, which will not influence the outcome as the primary objectives and endpoints are related to PK parameters, which will be evaluated with validated methods. Bioanalysis will also be done with validated methods. Based on previous PK experience, the sample size of 26 subjects in the fasting group and 18 subjects in the fed group will provide sufficient PK information as well as safety and tolerability data without exposing too many subjects. Study healthy subject demographics will represent a broader population of age (18 to 55 years old) and BMI (18 to 30 kg/m²). The treatment

schedule and dose of metformin has been chosen according to the standard treatment regimen applied for subjects suffering from T2DM. In China, the recommended daily dose prescribed for metformin is 2000 mg, whereas the average daily dose is approximately 1500 mg. There are 3 selections of strength for GIR tablets, 500, 850 and 1000 mg. Base on ethical consideration for the trial will be conducted on healthy subjects, and that the 500 mg GIR tablet is a commonly prescribed dose strength in China, the GIR 500 mg tablet is selected for this trial.

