6.1 Description of the Investigational Medicinal Products

All IMPs will be sourced from respective manufacturer as listed below (Table 3). The IMPs manufacturing process compliant with GMP requirements. The transportation and storage are to be tracked by temperature monitor to insure the medication quality and compliance to China regulation requirements.

 Table 3
 Information of Investigational Medicinal Products

Drug Treatment	Test IMP	Reference IMP
Formulation:	GIR 500 mg Tablet	GIR 500 mg Tablet
Manufacturer:	SASS., China	MSS, France
Expiry Date:	Refer to the label content	Refer to the label content
Storage Condition	According to medication label	According to medication label

GIR 500 mg = Glucophage 500 mg Immediate Release; IMP = Investigational Medicinal Product; MSS = Merck Santé s.a.s. in Semoy; SASS = Sino-American Shanghai Squibb Pharmaceuticals Ltd.

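### Is the 500 mg constant for CL/f and Vz/f on the wrong weight basis, because the tablet contains the hydrochloride salt?

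*SAP*

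**What the plan says.** SAP 16.3.2 defines CL/f as dose divided by AUC0→∞, and Vz/f as dose divided by the product of AUC0→∞ and λz. For CL/f it says "The dose amount to be used for this calculation is 500 mg". Later in the same section it gives the basis of that dose: "The dose amount for IMP administered is that of the active, free drug substance only, and is synonymous with the measured analyte". It continues "No adjustment for the dose amount value of IMP will be applied" wherever a formula needs a dose, which covers Vz/f.

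Protocol 3.2 describes the product differently. The "tablet contains metformin hydrochloride, a white to off-white crystalline compound", with the formula C4H11N5·HCl "and a molecular weight of 165.62". The same section also says "The active ingredient, metformin, is the main representative of the biguanide class antihyperglycemic drugs". Neither statement is tied to the 500 mg strength. Protocol 5.2 says only that "the 500 mg GIR tablet is a commonly prescribed dose strength in China", and Table 3 in Protocol 6.1 lists both products as "GIR 500 mg Tablet". Protocol 7.5 calls the analyte metformin and leaves the assay details to a separate analytical plan.

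SAP 16.2 makes CL/f and Vz/f secondary endpoints. Both are summarized descriptively; the model-based treatment comparison is extended only to AUC0→∞, and tmax has its own nonparametric comparison.

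**The concern.** A reader who goes from Protocol 3.2 to SAP 16.3.2 sees a salt in the tablet and a free-drug dose in the formulas, with no sentence linking them. If 500 mg is the weight of the hydrochloride and the laboratory reports metformin base, the numerator and denominator of CL/f are on different bases. The SAP would then have barred the adjustment that was needed.

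Such an error would also be quiet. It multiplies every subject's value by one constant, so CV% and GeoCV% do not change. The planned checks on the terminal fit and on the extrapolated area do not use the dose. At stake is the absolute level of two reported secondary parameters, which a later reader might compare with other metformin data.

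**Working it through.** **Inputs**

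- Calculation dose: 500 mg (SAP 16.3.2).
- Molecular weight of metformin hydrochloride: 165.62 (Protocol 3.2).
- Molecular weight of HCl: 36.461 (standard atomic weights H 1.008 and Cl 35.453; general constants, not in the documents).
- Formulas: CL/f = Dose / AUC0→∞; Vz/f = Dose / (AUC0→∞ × λz) (SAP 16.3.2). Both are proportional to dose.

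**The protocol's molecular weight**

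With C 12.011 and N 14.007, C4H11N5 = 4 × 12.011 + 11 × 1.008 + 5 × 14.007 = 129.167. Adding 36.461 gives 165.628, against the stated 165.62. The figure reproduces to within 0.008.

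**Base fraction of the salt**

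165.62 − 36.461 = 129.159, and 129.159 / 165.62 = 0.7799. So 500 mg of hydrochloride corresponds to 500 × 0.7799 = 389.9 mg of base.

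**Effect of using 500 mg, by case**

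| 500 mg strength | Concentrations | Error in CL/f and Vz/f |
|---|---|---|
| base | base (as the SAP states) | 0% |
| salt | salt | 0% |
| salt | base | 1 / 0.7799 − 1 = +28.2% |
| base | salt | 0.7799 − 1 = −22.0% |

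**Illustration of the third row**

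Take the reference AUC0→t of 8049.5 from the cited fasting study (SAP Table 1) in place of AUC0→∞, and assume units of ng·h/mL. With 500 mg, CL/f = 500,000,000 ng / 8049.5 = 62.1 L/h. With 389.9 mg it is 48.4 L/h.

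**Effect on any comparison**

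From the same study's geometric means, the test/reference ratio of CL/f is (D / 7946.5) / (D / 8049.5) = 8049.5 / 7946.5 = 1.013 for any dose D. The dose cancels. AUC0→t, Cmax and AUC0→∞ contain no dose term, and neither do tmax, t1/2, λz or AUCextra%. The 90% confidence intervals and the bioequivalence decision are therefore identical in all four cases.

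**The passages side by side**

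Protocol 3.2 says which compound is in the tablet. SAP 16.3.2 says what the 500 mg in the formula represents. These are different statements, and both can be true. Other wording fits the SAP: Protocol 5.2 speaks of the dose and the daily dose of metformin just before it lists the tablet strengths, and Protocol 8.1 and SAP 7.1 describe the products of the cited fasting study as 500 mg metformin tablets. This usage may be loose and does not prove a base-weight strength, but it gives no ground for calling the SAP sentence false.

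**The case for a change.** The strongest case for a change is that the SAP makes a factual claim that the rest of the documents do not confirm, and that the claim sits in text with signs of a template. The Vz/f formula has a stray operator, and the abbreviation list includes hazard ratio and partial response. The constant feeds two named secondary endpoints, a mismatch of 28% would be large beside ordinary reporting precision, and confirming the basis costs two look-ups.

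Part of this stands. The two passages are not reconciled, and the arithmetic is right if its premises are. The premises are the difficulty. An error needs two facts that the documents do not give: the weight basis of the strength and the basis on which concentrations are reported. Nothing in the text makes +28.2% more likely than zero, and the opposite mismatch is also open. Signs of template text do not show that this sentence is wrong.

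The argument that the error would stay hidden is also weaker than it looks. The SAP prints the dose and forbids any adjustment, so anyone who knows the two bases can rescale the reported values exactly with one multiplication. Replacing the constant before the bases are known could create the very error it is meant to prevent.

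**Conclusion.** The concern is a gap in documentation, not a demonstrated error. The SAP answers the question of basis in words; what is missing is a second source in these documents that confirms the answer. The possible effect on the absolute level of CL/f and Vz/f is 0% if the bases match, +28.2% if the strength is salt and concentrations are base, and −22.0% in the reverse case. These figures assume the printed molecular weight and standard atomic weights.

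The reach is small in every case. Both parameters are descriptive, test and reference carry the same factor, and no ratio, confidence interval, sample size or bioequivalence conclusion depends on the constant. This is a calculation constant only and does not concern the dose given to subjects. The pharmacokineticist who sets up the analysis can read the basis of the strength from the label and that of the concentrations from the analytical plan. Any change of number would rest on those sources, not on anything in the protocol or SAP. The gap is one that analysts fill sensibly, so the plan can stand as written.

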16.3.3 Analysis of PD Endpoints and Biomarker

Not applicable.

16.3.4 PK/PD Modelling and Simulation

Not applicable.

16.3.5 Analysis of Molecular Marker

Not applicable.

17 Safety Evaluation

Population: Safety Population

The subsections in this section include specifications for summarizing safety endpoints that are common across clinical trials such as adverse events, laboratory tests, ECG recordings and vital signs. Safety analyses will be done on the Safety Population. All safety data will be listed in individual subject listings by group, treatment sequence and subject.

All safety variables will be analyzed using descriptive statistics. For the evaluation of safety parameters, the continuous variables will be summarized descriptively by N, mean, median, SD, Q1-Q3, and minimum and maximum values. Categorical variables will be presented in frequency tables with the counts of observations and corresponding percentages.

17.1 Adverse Events

AEs will be coded using the MedDRA Version 20.1 or higher.

An AE will be considered as 'treatment emergent' if it occurred after the first IMP administration of each period or if it was present prior to first IMP administration but exacerbated after the first IMP administration of each period. All other adverse events will be considered 'pre-treatment'.

In the case where it is not possible to define an AE as TEAE or not, the AE will be classified as TEAE as the most conservative approach.

The AE listings will include the following items:

- System organ class
- Preferred term
- Investigator's description
- Whether the event is treatment-emergent
- Trial treatment at onset of event
- Date and time of onset and resolution

- Duration of the event
- Date and time of last administration before AE
- Study Day
- Severity
- Causality relationship to investigational product
- Outcome
- Action taken to investigational product
- Other action
- Seriousness

17.1.1 All Adverse Events

A summary table describing all the TEAEs occurring during the trial will be produced overall and by group as well as by treatment for each group using frequency of events and number and percentage of subjects experiencing these events overall and by SOC and PT.

Group/SOC terms will be sorted by decreasing total frequency. Preferred terms (PT) within each group/SOC term will likewise be sorted by decreasing total frequency.

In addition, all TEAEs will be tabulated by severity and relationship to IMP in the same manner.

Multiple occurrences of the same TEAE in one subject during the same treatment in the trial will be counted as multiple events in the frequency counts for adverse events. If a subject experiences more than one occurrence of the same AE during the same treatment in the trial, the subject will only be counted once for that treatment using the worst severity and the strongest relationship.

In case a subject had events with missing and non-missing severities, the maximum of the non-missing severities will be displayed. In case all the TEAEs of a subject are all with missing severities then Moderate will be used unless there is any evidence that it should be Severe.

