7.4.1 Adverse Events

7.4.1.1 Adverse Event Definitions

Adverse Event

An adverse event (AE) is any untoward medical occurrence in a subject or clinical investigation subject administered a pharmaceutical product, regardless of causal relationship with this treatment. An AE can therefore be any unfavorable and unintended sign (including an abnormal laboratory finding), symptom, or disease temporally associated with the use of a medicinal product, whether or not considered related to the medicinal product.

For surgical or diagnostic procedures, the condition/illness leading to such a procedure is considered as the AE rather than the procedure itself.

The Investigator is required to Grade the severity or toxicity of each AE.

Investigators must assess the severity of AEs according to the Qualitative Toxicity Scale, as follows:

GIR China Bioequivalence Study

Mild: The subject is aware of the event or symptom, but the event or symptom is easily

tolerated.

Moderate: The subject experiences sufficient discomfort to interfere with or reduce his or her

usual level of activity.

Severe: Significant impairment of functioning: the subject is unable to carry out his or her

usual activities.

Investigators must also systematically assess the causal relationship of AEs to IMP using the following definitions. Decisive factors for the assessment of causal relationship of an AE to the IMP include, but may not be limited to, temporal relationship between the AE and the IMP, known side effects of IMP, medical history, concomitant medication, course of the underlying disease, trial procedures.

Unrelated: Not reasonably related to the IMP. AE could not medically

(pharmacologically/clinically) be attributed to the IMP under study in this clinical

trial protocol. A reasonable alternative explanation must be available.

Related: Reasonably related to the IMP. AE could medically (pharmacologically/clinically)

be attributed to the IMP under study in this clinical trial protocol.

Adverse Drug Reaction

In accordance with GCP, adverse drug reaction (ADR) is an adverse event considered related to drug treatment.

Abnormal Laboratory Findings and Other Abnormal Investigational Findings

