8.5 Description of Statistical Analyses

8.5.1 General Considerations

Details of the statistical analysis will be presented in a statistical analysis plan prior to database lock.

The statistical analysis will not be started until all data have been corrected and checked for plausibility, and until all necessary coding and assessments have been completed.

All data recorded during the trial will be presented in individual data listings performed on the Safety Population. All data will be evaluated as observed values; no imputation method for missing values will be used. Methods for concentration data below the lower limit of quantification will be described in the statistical analysis plan. The consideration of covariates in the mixed effect model is not planned.

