7.2 Randomization

Each eligible subject will be allocated to a treatment sequence according to a computer-generated randomization schedule. Subjects will be identified only by their assigned subject number. The subjects will receive consecutive subject numbers in the order of their enrollment into the trial.

A total of 44 eligible healthy male and female Chinese subjects (26 in fasting state and 18 in fed state, Table) who meet the eligibility criteria will be randomized (with each gender representing no less than 1/4 of the total number within each group) on Day 1, in a 1:1 ratio to 1 of 2 treatment sequences: Sequence A-B or Sequence B-A as presented in Table .

In sequence A-B, subjects will receive test GIR tablets (Treatment A) in Period 1 and reference GIR tablets (Treatment B) in Period 2. In sequence B-A, subjects will receive reference GIR tablets in Period 1 and test GIR tablets in Period 2 after Washout.

Table 5 Randomization Allocation

| | Day 1 of Period 1 | Day 1 of Period 2 |
|-----------------------|---------------------|---------------------|
| Fasting group (n= 26) | Treatment A (n= 13) | Treatment B (n= 13) |
| | Treatment B (n= 13) | Treatment A (n= 13) |
| Fed group (n= 18) | Treatment A (n= 9) | Treatment B (n= 9) |
| | Treatment B (n= 9) | Treatment A (n= 9) |

Subjects will only be replaced if the number of subjects within each group falls below 20 (fasting) or 12 (fed). The subject who is replacing a discontinued subject will then be allocated to the treatment sequence of the subject who discontinued.

8 Overview of Planned Analyses

The methods described in this document will be applied to the preparation of tables, figures and listings (TLFs). Statistical analyses will be performed using cleaned electronic clinical report form (eCRF) data collected.

This SAP will cover the final analysis only. The final analysis will be performed only after the last subject has completed the study with all study data in-house and all data queries resolved. The SAP will be finalized prior to database lock.

9 Changes to the Planned Analyses in the Clinical Trial Protocol

The Screening Population has been added to include all subjects who signed informed consent in the study.

10 Protocol Deviations and Analysis Sets

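### SAP 17.1.1 imputes Moderate when all of a subject's TEAE severities are missing, against protocol 8.5.1, and lets a known Mild event lower the displayed worst severity

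*SAP*

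**What the plan says.** SAP 17.1.1 tabulates TEAEs by severity for each food group and treatment, overall and by system organ class and preferred term. When the same AE recurs in a subject under the same treatment, "the subject will only be counted once for that treatment using the worst severity and the strongest relationship".

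Two sentences on missing grades follow:

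- Some grades known, some missing: "In case a subject had events with missing and non-missing severities, the maximum of the non-missing severities will be displayed".
- No grade known: "In case all the TEAEs of a subject are all with missing severities then Moderate will be used", with the exception "unless there is any evidence that it should be Severe".

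Four other places bear on this:

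- Protocol 8.5.1: "All data will be evaluated as observed values; no imputation method for missing values will be used".
- SAP Section 9, the list of changes from the protocol, has a single entry: "The Screening Population has been added to include all subjects who signed informed consent in the study".
- SAP Section 11, on qualitative variables, keeps missing observations in the denominator and shows them as a category of their own, unless otherwise stated. The laboratory, vital-sign and ECG frequency tables (SAP 17.3, 17.4, 17.5.1) include a Missing class.
- Protocol 7.4.1.1 sets a three-level scale (Mild, Moderate, Severe) and says "The Investigator is required to Grade the severity or toxicity of each AE".

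**The concern.** There are two faults in the same pair of sentences.

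First, the same missing grade is treated in two incompatible ways. Standing alone, it counts as at least Moderate. Beside any graded event, it counts for nothing. A summary of worst severity should never fall when an event is added, and this one can.

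Second, the Moderate value is not observed. Filling it in is an imputation, which the protocol excludes for all data. The SAP gives no reason for the exception and does not list it as a change. The step up to Severe depends on evidence for which the SAP defines no standard, assessor or timing, in a trial where treatment is known.

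What is at stake is the accuracy and reproducibility of one descriptive safety table. The sentences also do not say whether they apply per term, per treatment or across the whole trial, so two programmers could produce different tables from the same data.

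**Working it through.** The plan states no figure to reproduce here. The check is to write the rule down and apply it.

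**Rule, from SAP 17.1.1.** Let K be the set of known grades among the events considered, ordered Mild < Moderate < Severe.

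- If K is not empty, display max(K).
- If K is empty, display Moderate, or Severe if there is evidence for it.

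**Enumeration.** Start from every set of one or two events, add one more event of any grade, and look for cases where the displayed grade falls. The Severe exception is attached only to the sentence for the all-missing case, so mixed cases are taken to follow the other sentence. These are all the cases found:

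| Events before | Displayed | Event added | Displayed after |
|---|---|---|---|
| Missing | Moderate | Mild | Mild |
| Missing, Missing | Moderate | Mild | Mild |
| Missing, with evidence | Severe | Mild | Mild |
| Missing, with evidence | Severe | Moderate | Moderate |
| Missing, Missing, with evidence | Severe | Mild | Mild |
| Missing, Missing, with evidence | Severe | Moderate | Moderate |

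No drop occurs when the starting set already holds a known grade. The fault therefore comes entirely from the value given to the all-missing case.

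**Scope.** The recurrence rule is limited to the same AE under the same treatment. The two missing-grade sentences speak only of a subject. Three readings are possible:

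- Same term, same treatment: the drop needs a graded Mild occurrence of that same term under that same product.
- Any event, same treatment: any Mild event under that product is enough.
- Any event in the trial, the literal wording: a Mild event under one product could set the grade shown for an ungraded event under the other.

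The drop is possible on all three readings and least frequent on the first.

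**Against the protocol and the SAP's own default.** Protocol 8.5.1 covers all data and excludes imputation. SAP 17.1.1 substitutes Moderate. SAP Section 9 declares only the Screening Population. The default in SAP Section 11 would have given a Missing category.

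**Weight of one subject.** Using the planned group sizes in protocol 5.1, 1/26 = 3.8% (fasting) and 1/18 = 5.6% (fed). This is the weight of one reclassified subject in a severity row, not an estimate of how many there will be.

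**The case against.** The strongest reply is that the rule will hardly ever be used and hides little when it is. The investigator must grade every AE, severity is a required eCRF item (protocol 7.4.1.2), and analysis waits until data are checked and queries resolved. All of that stands and keeps the point small.

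Four stronger readings are tempting, and the documents do not support them.

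- *The rule conceals severe events.* SAP 17.1 lists each AE with its severity, seriousness, outcome and action taken. SAP 17.1.2 and 17.2 list discontinuations, deaths and SAEs separately. SAP Section 11 requires imputed information to be flagged in listings. Only the per-subject count is affected.
- *A subject's grade depends on unrelated events.* That follows only on the wider readings of scope. On the narrowest, the other event is the same term under the same product.
- *The rule should have been conservative, as SAP 17.1 is for unknown treatment emergence.* That would mean imputing Severe, which cannot be asked for alongside the objection to imputing at all. SAP 17.1 also concerns a different question.
- *Both sentences should go.* Showing the known maximum in mixed cases uses observed data and can stay.

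It may also be said that Section 11's default yields where the SAP states otherwise, so severity is formally a permitted exception. That is so within the SAP. It does not reconcile the rule with the protocol, nor supply the missing entry in Section 9. The Severe exception does not help either: its evidence is undefined, and its wording does not reach the mixed case.

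**Conclusion.** The point holds and is minor. As written, the all-missing sentence imputes a grade that the protocol excludes, departs without explanation from the SAP's usual treatment of missing categories, and is undeclared. Together with the mixed-case sentence, it allows the displayed worst severity to fall from Moderate to Mild, or from Severe where the exception has been used, when a known lower-grade event is added.

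The size is one subject at a time in a descriptive table: 3.8 percentage points of 26 or 5.6 of 18. This assumes the planned group sizes as denominators. The documents give no basis for a count of missing grades, which is expected to be very small. Bioequivalence, which rests on AUC and Cmax, is unaffected.

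**What to change.** In SAP 17.1.1:

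1. Delete the sentence that assigns Moderate, with its Severe exception. Count a subject with no known grade in a Missing severity row.
2. Keep the known maximum for mixed cases, and flag or footnote subjects who also have an ungraded event.
3. State that the rule applies within treatment, at the level being tabulated (same AE term, system organ class or overall).

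If the sponsor prefers to impute, apply one rule to each ungraded event before taking the maximum, so that adding an event cannot lower the result, and declare it in SAP Section 9 as a departure from protocol 8.5.1.

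The cost is a small wording change, one row and a footnote in the severity table shell. No new data are needed.
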